For all participants, treatment will continue until radiographic disease progression, intolerance to trial intervention, risk to participant (including clinical progression) as determined by the Investigator and/or Sponsor, consent withdrawal, start of a non-trial anticancer treatment, major protocol noncompliance that would jeopardize participant safety and/or data interpretation as determined by the Sponsor, pregnancy, or death. For participants with progression based on tumor markers per GCIG or PCWG3 criteria, evidence of radiographic and/or other signs of clinical progression should be used in determining treatment decisions. Participants requiring more than 3 continuous weeks off planned trial treatment for any reason will be discontinued unless the Investigator in agreement with the Sponsor believes that the participant would derive clinical benefit with continued treatment.

Participants are allowed to continue treatment after disease progression if the Investigator deems that it is in the participant's best interest. Participants in Arm 1 will have the opportunity to continue treatment post-progression with the combination of RP-3467 and olaparib (up to the highest dose level of the combination deemed safe and tolerable and cleared by the SRC, but dependent on the participant's overall tolerability of RP-3467 monotherapy). In all cases of treatment post-progression, the participant will be required to provide signed written consent agreeing to treatment after disease progression. [REDACTED]

Eligibility Criteria

Inclusion Criteria:

To be eligible to participate in this trial, an individual must meet all the following criteria:

1. Written informed consent, according to local guidelines, signed and dated by the participant or legal guardian prior to the performance of any trial-specific procedures, sampling, or analyses. Participants with impaired decision-making capacity must have a close caregiver or legally authorized representative (LAR) present.
2. Male or female participants ≥ 18 years of age at the time of signing the informed consent
3. Eastern Cooperative Oncology Group (ECOG) performance status of 0 or 1
4. Participant must have one of the following that has progressed or was non-responsive to prior systemic therapy and for which no standard or available known therapeutic option exists:

- a. locally advanced or metastatic epithelial ovarian cancer (including fallopian tube or primary peritoneal), or
- b. metastatic breast cancer, or

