12.1.2 Response Evaluation Based on Prostate Cancer Working Group 3 Criteria

The Response Evaluation Criteria in Solid Tumors (RECIST) guidelines (version 1.1) are outlined in Section 12.1.1 and will be utilized for evaluation of response in participants with prostate cancer with measurable and non-measurable disease involving soft tissue lesions. A modification from standard RECIST v1.1 is that bone lesions will not be recorded as target or non-target lesions for the assessment.

In addition to RECIST v1.1, participants with prostate cancer will be evaluated by the Prostate Cancer Working Group (PCWG3) criteria for assessment of bone progression and prostate-specific antigen (PSA) response as described by Scher 2016.

Bone Lesions

The presence or absence of bone metastasis will be assessed at baseline by ^{99m}Tc -methylene diphosphonate radionuclide bone scintigraphy. The total number of bone lesions will be recorded.

Assessment for progression:

- A minimum of two or more new lesions compared with the baseline bone scan after the 12-week flare window.
- If the new lesions occur within the first 12 weeks of treatment, assessment of progression requires a confirmatory scan performed 6 or more weeks later showing two additional new lesions compared with the first follow-up scan to rule out pseudoprogression (2 + 2 rule).
- If at least two additional new lesions are seen on the next (confirmatory) scan performed after the 12-week flare window, the date of progression is the date of the first post-treatment scan, when the first two new lesions were documented.
- Changes in intensity of uptake alone do not constitute either progression or regression.

PSA

For participants with nonmeasurable disease, PSA measurements will be used to assess response. To be evaluable for PSA response PSA levels must be > 2 ng/mL at the most recent assessment and must be rising as determined by a sequence of increasing values at a minimum of 1-week apart prior to treatment start.

Assessment for response:

- Confirmed PSA response is defined as $\geq 50\%$ reduction in PSA from baseline to lowest post-baseline PSA result, with a consecutive assessment conducted at least 3 weeks later.

Assessment for progression:

- PSA progression is defined as a PSA increase $\geq 25\%$ and $\geq 2\text{g/mL}$ above the nadir (or baseline for participants who did not have a decline in PSA), confirmed by a second increasing value at least 3 weeks later.

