- A PSA rise within the first 12 weeks of therapy in the absence of evidence of confirmed radiologic progression will not be used as a criterion for progression.

12.1.3 Gynecological Cancer Intergroup Definitions for Response and Progression in Participants with Ovarian Cancer

For participants with ovarian cancer with elevated CA-125 levels, response evaluation will include cancer antigen 125 (CA-125) in addition to Response Evaluation Criteria in Solid Tumors (RECIST) v1.1 criteria as per Gynecological Cancer Intergroup (GCIG) criteria (Rustin 2011).

Definition of Response by CA-125

- A $\geq 50\%$ reduction in CA-125 levels from a pretreatment sample. The response must be confirmed and maintained for at least 3 weeks (note that GCIG recommends maintenance for at least 28 days; a modification was made based on the 3-week cycle length in this trial). Participants can be evaluated for a CA-125 response only if they have a pretreatment sample that is at least twice the upper limit of the reference range and within two weeks before starting treatment.
- Intervening samples and the confirmatory sample must be less than or equal to the previous sample (within an assay variability of 10%).
- The date when the CA-125 level is first reduced by 50% is the date of the CA-125 response.
- A CA-125 complete response can occur if CA-125 levels fall to within the reference range.

Definition of Progression by CA-125

- For participants with elevated CA-125 pre-treatment that normalizes or for participants with CA-125 in the normal range at baseline: CA-125 at least 2 times the upper limit of the reference range on 2 occasions at least 1 week apart.
- For participants with elevated CA-125 pre-treatment which never normalizes: CA-125 at least 2 times the nadir value on 2 occasions at least 1 week apart.

- Progressive disease (PD) by objective change in tumor size should always take precedence over changes in CA-125 should it occur first. If measurable disease is reducing in size but the CA125 suggests progression the participant should remain on treatment.
- CA-125 progression will be assigned the date of the first measurement that meets the above criteria.

Note: CA-125 progression in the absence of radiographic or other clinical evidence of progression will not be sufficient criteria for treatment discontinuation in this trial.

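### The PSA progression rule in SAP 12.1.2 prints its absolute rise in g/mL while the same subsection measures PSA in ng/mL, so the rule as printed cannot be met.

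*SAP*

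**What the plan says.** SAP 12.1.2 applies PCWG3 criteria to participants with prostate cancer, in addition to RECIST v1.1. Its PSA paragraphs contain two absolute thresholds:

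- **Evaluability for PSA response:** "PSA levels must be > 2 ng/mL at the most recent assessment", with a rising sequence before treatment.
- **PSA progression:** "PSA progression is defined as a PSA increase $\geq 25\%$ and $\geq 2\text{g/mL}$ above the nadir". Baseline replaces the nadir if PSA never fell, and a second increasing value at least 3 weeks later must confirm the rise.

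The next bullet sets aside PSA rises in the first 12 weeks unless there is confirmed radiologic progression. No other place in the available protocol or SAP text restates the PSA progression threshold or corrects its unit.

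The protocol synopsis (section 1.1, Overall Design) refers to marker progression in one sentence. It begins "For participants with progression based on tumor markers per GCIG or PCWG3 criteria" and continues that "evidence of radiographic and/or other signs of clinical progression should be used in determining treatment decisions".

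**The concern.** The two PSA thresholds carry the same number, 2, but units that differ by a factor of one billion. The progression threshold is part of an operative definition, and a SAP is the specification that derivation programs are written and validated against.

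The definition has a place in this trial. Metastatic castration-resistant prostate cancer is one of four eligible tumor types. Inclusion criterion 5 can admit participants with non-measurable disease, including those with elevated tumor markers. SAP 12.1.2 does not record bone lesions as RECIST target or non-target lesions. For some prostate participants, PSA and the bone scan may therefore carry much of the disease assessment.

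Under the printed unit, no one could reach the protocol's category of marker progression through PSA. The 12-week exclusion would also have nothing to act on.

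**Working it through.** **Inputs**

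- Relative rise: at least 25% (SAP 12.1.2).
- Absolute rise: at least 2 g/mL as printed (SAP 12.1.2).
- Unit for PSA elsewhere in the subsection: ng/mL (SAP 12.1.2, response evaluability).
- Connector: 'and', so both conditions must hold.
- Nadir: the documents give no PSA values. The range of 2 to 10,000 ng/mL below is an assumption.

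**Step 1: convert the printed threshold.** 1 g = 10^9 ng, so 2 g/mL = 2 × 10^9 = 2,000,000,000 ng/mL. The ratio to 2 ng/mL is 10^9.

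**Step 2: PSA needed for progression.** With both conditions required,

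required PSA = nadir + max(0.25 × nadir, absolute rise).

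| Assumed nadir (ng/mL) | Required if the unit is ng/mL | Required as printed (ng/mL) | Multiple of nadir as printed |
|---|---|---|---|
| 2 | 4 | 2,000,000,002 | 1,000,000,001 |
| 8 | 10 | 2,000,000,008 | 250,000,001 |
| 10 | 12.5 | 2,000,000,010 | 200,000,001 |
| 100 | 125 | 2,000,000,100 | 20,000,001 |
| 1,000 | 1,250 | 2,000,001,000 | 2,000,001 |
| 10,000 | 12,500 | 2,000,010,000 | 200,001 |

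**Step 3: where each condition governs.** The two conditions are equal when 0.25 × nadir = absolute rise.

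- In ng/mL: nadir = 2 / 0.25 = 8 ng/mL. The floor of 2 governs below 8 and the 25% rise governs above it, so both have a role.
- As printed: nadir = 2 × 10^9 / 0.25 = 8 × 10^9 ng/mL. The 25% condition never decides anything.

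**Step 4: one illustrative participant (assumed values).** The nadir is 4 ng/mL, followed by 12 and then 20 ng/mL three weeks apart, both after week 12. The rises are 12 − 4 = 8 ng/mL (8/4 = 200%) and 20 − 4 = 16 ng/mL (16/4 = 400%). In ng/mL the requirement is 4 + max(1, 2) = 6, so the first value meets it and the second confirms it. As printed, the same participant does not progress.

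**The case against.** Four points on the other side carry weight.

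1. **Origin.** In the machine-read text the unit sits inside a converted formula string, and other single-letter misreadings occur in these documents (the BOIN name, for example, is garbled in one place). A lost 'n' cannot be excluded. This stands: the source PDF has to be checked before the slip is attributed to the authors.
2. **Practical risk.** The subsection names PCWG3 and gives PSA in ng/mL. A programmer who compares PSA recorded in ng/mL with the number 2 obtains the workable rule. The failure needs someone to apply the printed unit literally. This also stands. It makes the point a correction rather than a design flaw, but it does not make the text right.
3. **Analysis consequences.** A reader might infer that disease control or progression-free time will be overstated in prostate participants. The documents do not show this. SAP sections 7 to 9 are not in the available text, PFS and CBR appear only in the abbreviation list, and section 12.1.2 invokes PCWG3 for bone progression and PSA response. PSA response, a fall of at least 50%, does not use this threshold. A reader might also infer that every rising PSA is misclassified. In ng/mL, too, a rise below 25%, an unconfirmed rise, or an early rise without confirmed radiologic progression is not PSA progression.
4. **Treatment consequences.** A reader might infer that participants would stay on treatment wrongly. The protocol synopsis rests treatment decisions after marker progression on radiographic and/or other clinical signs, which limits any such effect.

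None of this removes the conflict between the two units.

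**Conclusion.** The point holds as a unit inconsistency in an operative definition. As printed, the absolute condition is 10^9 times the corresponding value in ng/mL, and because of the 'and' the rule cannot be met at any nadir in the assumed range of 2 to 10,000 ng/mL. The ng/mL reading comes from the subsection itself and needs no outside source.

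The reach is narrow. Only PSA progression in prostate participants is affected. RECIST progression, bone-scan progression and PSA response keep their own criteria. The primary endpoints are DLTs and TEAEs (SAP 3.2.1), dose escalation runs on DLTs (SAP 2.1), and the analysis is descriptive (SAP section 5). Any bias in an efficacy summary rests on two conditions that the available text does not establish: that PSA progression feeds such a summary, and that the threshold is programmed literally. The conclusion also assumes that the source PDF shows the unit as read here.

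**What to change.** - Check the PSA progression bullet of SAP 12.1.2 in the source PDF.
- If it reads g/mL, change the absolute rise to ≥ 2 ng/mL, matching the unit already used in that subsection.
- Confirm that the PSA progression derivation, any eCRF edit check and any copy of this text in a protocol appendix use ng/mL.
- Make the correction before database lock, so that the program and its specification agree without an undocumented reinterpretation.

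The cost is one corrected unit and a short check of the program and forms. No additional data and no change of design are needed.
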